Prior to initiation of the study, the research nurse will hold an in-service for clinical staff to alert them of the study. A specific research sticker will be placed in the chart to alert clinical staff that the patient is enrolled in this research study. The MD responsible for the care of the patient will write the orders for the supplements. The Pharmacy will prepare all supplements and the nurses will administer them.

C. Data Collection

Plasma and urine Se and plasma Gpx will be measured weekly from the time of admission for a maximum of 8 weeks or until the patient achieves 95% definitive wound closure.

The research nurse will obtain 4 ml or 8ml (8 ml will be drawn instead of 4 ml every other week starting with week 1 for real time analysis) of whole blood off an existing catheter and place it into a trace-element free blood collection tube.

Every other week, when 8 ml of blood is needed, 4 ml will be transferred by the unit assistant to the MGH laboratory for immediate analyses (the MGH lab uses Quest Labs for analysis of selenium). If in the unlikely event that the MGH lab rejects the sample for any reason, another 4 mL blood draw will be collected and sent to the MGH lab for real-time analyses.

Weekly, the 4 ml sample will be transported by the nurse to the clinical research lab (in the same building). In the lab the nurse will use a centrifuge to separate the blood and then pipette the plasma and whole blood into collection vials to be frozen prior to analyses. A 24 hour urine will be initiated the day prior to blood sampling for analysis of urinary Se. Urine will be collected via an existing catheter. If no catheter exists patient will be asked to urinate into a container. If the patient is unable to urinate into a container, the urine sample will not be collected. Infant urine will be collected via diapers. The research nurse will then bring the urine container down to the clinical research lab and aliquot it into 50 ml vials prior to being frozen. Frozen samples are eventually mailed to a commercial laboratory for lab analyses. The PI is certified to ship biological products and all appropriate regulations will be followed.

Culture Data

Wound cultures will be obtained for all patients admitted to the acute care unit at Shriners Burns Hospital, per routine care, on admission. Urine cultures will also be obtained upon admission if one or more of the following criteria are met:

- Symptoms of urinary tract infection (UTI)

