The pathogenic fungi (Histoplasma and Blastomyces) cultures will be referred to the MGH laboratory for speciation. Results are confidentially reported to the medical team at Shriners Burns Hospital.

Normal flora cultured from the sputum (viridians strep Neisseria species, coagulase negative Staphylococcus and rare amounts of yeast, enteric gram negatives, Staph. aureus.) will be documented as normal flora)

Dietary Data

Dietary data (enteral nutrition, parenteral nutrition, oral intake) will be collected daily from the medical record. Total Se intake via supplements and/or enteral feedings will be calculated based on daily intake and output sheets as recorded by the bedside nurse. Dietary Se intake from food will be determined using the Nutrient Database System for Research version 2005.

Other Data

Weights will be obtained as part of routine care by the bedside nurse, and recorded twice a week. Demographic data will be obtained from the medical record. Please see data collection sheet for details.

As part of routine care by the medical team neurological status will be assessed and several laboratory values will be monitored closely (including total protein, albumin, prealbumin and C-reactive protein complete blood count, serum creatinine, AST, ALT, alkaline phosphatase, total bilirubin, and coagulation studies) will be recorded from the medical record.

D. Selenium Analysis

Blood (4 ml or 8 ml) and urine samples will be obtained weekly. De-identified samples will be sent to a commercial laboratory for analyses. Results will be sent to Shriners Burns Hospital in Boston. Additionally, to ensure the safety of all patients, once every 2 weeks, blood samples (4 ml) will also be sent to the Massachusetts General Hospital Chemistry lab for analysis. These results are typically available after 24-48 hours.

The study endpoint will be whichever of the following factors happens first:

- 8 weeks
- discontinuation of central venous catheter
- a stop in Se/Placebo infusion lasting longer than 48 consecutive hours or 72 hours in 1 week,
- when the patient achieves 95% definitive wound closure determined by the attending physician.

No interim analyses are planned. Data obtained from our previous investigation on Se and pediatric burns was used for the power analysis calculation:

$$n = (2 \times [Z_{(1-\alpha/2)} + Z_{(1-\beta)}]^2) / \Delta^2$$

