where $Z_{(1-\alpha/2)}$ and $Z_{(1-\beta)}$ represent percentage points of the normal distribution for statistical significance level and power, respectively. The values used were 1.96 for a significance level of 5% and 0.8416 for a power of 80%. The Δ represents the standardized difference (the treatment difference divided by its standard deviation). This was calculated by subtracting the mean plasma Se determined in our pilot study (1.08 $\mu\text{mol/L}$) from the average plasma Se of healthy American children 1.35 ($\mu\text{mol/L}$) and dividing by the standard deviation (0.34). This calculation revealed that 25 subjects are needed per group to obtain 80% power and a significance level of 5%.

All subjects enrolled will be included in the statistical analyses (intent-to treat). A 2-sided statistical test will be used for all analyses and the overall type-I error rate will be controlled at the 5% level. For each dependent variable (plasma selenium, urinary selenium, plasma GPx activity) a 2-way repeated measures ANOVA will be used to examine the difference among groups and over time (primary hypothesis). Tukey's will be utilized as the post-hoc test.

An ordinal logistic regression will be performed to determine the relationship between the incidence of infection (categorized by burn, bloodstream, urinary tract infection, and PNA) and plasma selenium, urinary selenium, plasma GPX, age, initial percent TBSA burned, and treatment group (secondary hypothesis).

Appropriate confounding factors (including but not limited to dietary Se intake, age, sex, race, initial %TBSA, and length of time from burn injury to study enrollment) will be included in the statistical models. All statistics will be completed using SAS software.

VI. Risks and Discomforts

Phlebotomy will be minimal (4 or 8 ml/wk) and will be obtained painlessly through existing catheters or during operative procedures.

Se toxicity is rare. Symptoms include:

- memory loss
- gastrointestinal upset,
- hair loss,
- weakened nails,
- white blotchy nails,
- garlic breath odor,
- metallic taste,
- vomiting,

- sweat
- dermatitis,
- dental defects,
- nervousness,
- mental depression,
- fatigue,
- irritability,
- mild nerve damage,
- Peripheral vascular collapse,
- Internal vascular congestion,
- Hemorrhage,
- Congested and edematus lungs,
- Brick-red color gastric mucosa
- Coma
- Death

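### The primary repeated measures ANOVA is not specified for weekly series that end at child-specific times, so the plan does not say how its all-enrolled promise will be met

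*Combined protocol and SAP*

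**What the plan says.** All references are to the combined protocol and SAP.

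- **Population (V.D, statistical text).** "All subjects enrolled will be included in the statistical analyses (intent-to treat").
- **Primary test (V.D).** For plasma selenium, urinary selenium and plasma GPx, "a 2-way repeated measures ANOVA will be used to examine the difference among groups and over time (primary hypothesis"). Tukey's method "will be utilized as the post-hoc test".
- **Software (V.D).** "All statistics will be completed using SAS software". No procedure is named.
- **End of measurement (V.C, Data Collection).** Samples are taken weekly "for a maximum of 8 weeks or until the patient achieves 95% definitive wound closure". A urine sample is skipped if the child has no catheter and cannot void into a container.
- **End of study (V.D).** "The study endpoint will be whichever of the following factors happens first": eight weeks, "discontinuation of central venous catheter", "a stop in Se/Placebo infusion lasting longer than 48 consecutive hours or 72 hours in 1 week", or 95% wound closure.
- **After removal (III and V.B).** Blood and urine sampling stops when a child withdraws, meets an exclusion criterion during the study, or is removed for a long infusion hold.

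No section gives a missing-data method, a mixed or likelihood-based model, a covariance structure or the number of weekly levels in the test. The sentence on confounders in V.D does not deal with incomplete series.

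**The concern.** Series of unequal length follow from the protocol's own rules, so a complete eight-week record cannot be taken as the norm. The named test suits such data poorly in both of its usual forms:

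- **Multivariate form, one row per child.** Every child with a missing week is dropped. This would contradict the intent-to-treat sentence and leave a group selected after randomisation. Wound closure and line removal plausibly follow recovery, so that group would lean towards slower healers.
- **Univariate form, one row per sample.** Partial series are kept, but with unbalanced data the F-tests are only approximate.

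The population sentence says which children count. It does not say how a child with three weekly values enters a test that may have up to eight levels. That choice, and the number of weeks, would be left until the data are in hand. At stake is the precision of the primary comparison.

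**Working it through.** **1. The plan's own sample size.** Inputs from V.D: means 1.08 and 1.35 µmol/L, SD 0.34, z-values 1.96 and 0.8416.

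Δ = (1.35 − 1.08)/0.34 = 0.27/0.34 = 0.794

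n = 2 × (1.96 + 0.8416)² / 0.794² = 24.89, rounded up to 25 per group. Power at 25 is 0.802.

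The stated figure reproduces. It is a single two-group comparison with no allowance for incomplete series.

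**2. Share of children with a full series.** The documents do not give it. As an assumed proxy I use pilot length of stay from I.B, Table 4: 50 ± 40 days, range 11-161, 20 children. Four distributions were matched to that mean and SD, two of them shifted to start at 11 days.

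| Fit | Share reaching day 56 | Children per arm (× 25) |
|---|---|---|
| Lognormal | 0.304 | 7.6 |
| Gamma | 0.341 | 8.5 |
| 11 + lognormal | 0.277 | 6.9 |
| 11 + gamma | 0.314 | 7.8 |

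The proxy can err either way. Line removal, wound closure or an infusion stop can precede discharge, which shortens series. The entry threshold here (≥ 20% TBSA, against above 15% in the pilot) may lengthen them.

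**3. Power if only completers are kept.** With W weeks and an assumed common within-child correlation r, the SD of a child's mean is 0.34 × √[(1 + (W − 1)r)/W].

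- W = 8, r = 0.8: 0.34 × √(6.6/8) = 0.309
- W = 8, r = 0.3: 0.34 × √(3.1/8) = 0.212

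At 7.6 children per arm and r = 0.8, the noncentrality is 0.27 / (0.309 × √(2/7.6)) = 1.70. With pooled error from three arms, power is about 0.37. Over the four fits, at fixed arm sizes, this gives 0.34-0.41 at r = 0.8 and 0.61-0.71 at r = 0.3.

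Simulation lets the number of completers vary by chance and gives slightly less: 0.32-0.40 and 0.57-0.68. Allowing for simulation error, that is roughly 30-40% and 55-68%.

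**4. Fewer weekly levels.** The plan does not fix eight. With three levels, 19-22 children per arm would be complete, and completer power at r = 0.8 is about 70-79%.

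**5. Analyses that keep partial series.** Same fits and eight-week window, placebo against one selenium arm, unadjusted.

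| Analysis | r = 0.8 | r = 0.3 |
|---|---|---|
| Mixed model, group × week, equal-weight average over weeks | 82-84% | 96-97% |
| Simple mean of each child's available weeks | about 82-86% | 96% or more |

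These can exceed 80% because averaging several weeks reduces the SD below the 0.34 used in the plan's formula. With Tukey adjustment over three arms, the mixed model has 70-73% and eight-week completers 20-25% at r = 0.8.

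All figures assume a constant effect over time and time on study unrelated to selenium.

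**The case against.** The strongest reply is that the plan has already settled who is analysed. An analyst who kept only completers would break a written rule, and deletion belongs to one computing form of the test. The pilot report in I.B counts percentages of all weekly samples, which suggests, without proving it, that the team works with every available value. This largely stands. A reader might infer that the plan will drop children or breaks intent-to-treat; the text does not support that. What is open is the method of estimation and the number of weeks.

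A second reply is that the low power figures need three things at once: deletion despite the population sentence, eight required levels, and length of stay as a fair proxy. That also stands, so the figures are illustrative. Nor does the loss come from lacking a mixed model, since simple child means keep the power too. It comes from deletion.

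Two further readings are tempting. One is that the results would be biased between arms. That would require healing or removal to differ by arm, and nothing in the documents allows it to be sized. The other is that V.C and V.D contradict each other on when measurement ends. They do not: the four events in V.D include both of those in V.C, and the first to occur applies.

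None of this supplies the missing specification. Keeping all partial series in the univariate ANOVA still leaves approximate tests.

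**Conclusion.** The point holds as a gap in the primary analysis: incomplete series are built in, the named test handles them poorly in either form, and the plan does not choose between the forms or fix the number of weeks. That conclusion rests on the text alone.

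The size is conditional on the length-of-stay proxy, the assumed correlations, a constant effect and time on study unrelated to selenium. Under those assumptions the worst reading, eight-week completers only, could cut power to less than half of the planned 80% at a correlation of 0.8. With three weekly levels the loss is modest, and with partial series kept there is none on the unadjusted comparison. The calculation shows loss of precision and says nothing about bias. This is a cheap improvement to the wording, not evidence that the trial would be analysed wrongly.

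**What to change.** In V.D, specify the primary analysis as follows:

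1. Use a likelihood-based mixed model with group, week and group × week, on every available on-study weekly value from every randomised child.
2. Name the group contrast and the number of weeks it covers, chosen so that the sparse late weeks can support it. Keep the Tukey-adjusted group comparisons.
3. Pre-specify a parsimonious covariance structure, such as AR(1) or compound symmetry, with a fallback. An unstructured matrix over eight weeks has 8 × 9/2 = 36 parameters, and under the proxy only about 21-26 children across all three arms would reach week 8.
4. State whether weeks after wound closure are missing or outside the question.
5. Describe the population as all randomised children with available on-study data, and report removals by arm and reason.
6. Cross-reference the ends of measurement in V.C and V.D. Leave the infusion and removal rules unchanged.

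The cost is plan wording and slightly more analysis work, with no new visits, data or blood draws. The downside is that the model relies on values being missing at random after each child's series ends, which the plan should state.

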subjects/parents/ guardians at the bedside, who meet the inclusion/exclusion criteria, with a brief explanation of the study. A more detailed explanation will be offered in a private room to those interested in participation. The alternative to participation is “not to participate”. Care will not be altered for patients who do not participate. Informed consent will be obtained if the patient and/or parent/legal guardian agrees to participate. Parents/legal guardians will be allowed an indefinite amount of time for questions and participation consideration. Parents/legal guardian will provide consent for 0-18 year old children (documented in writing using the PHRC approved consent form). The permission of both parents is required unless one parent is deceased, unknown, incompetent, or not reasonably available or if only one parent has legal responsibility for the care and custody of the child. Any child 14 years or older, who is able, will consent along with parent/guardian. The assent of each child (age 7 and older) who is capable of providing assent based on medical condition, age, maturity, and psychological state will be sought. According to a power analysis calculation, 75 children will be included in this study.

B. Treatment Assignment and Randomization

This is a randomized, double-blind, placebo-controlled trial. Patients will be randomly assigned to receive Selenium supplementation (either 2, or 4 ug/kg/day) or a placebo. 25 subjects will be in each group (total of 75 subjects). Randomization will occur by using a computerized randomization list. A pharmacist, who is not a member of the study staff, will prepare the supplements and label them accordingly prior to distribution.

V. Study Procedures

A. Study Parameters

- B. Lab studies conducted solely for the purpose of this study include plasma and urinary Se, plasma Gpx and dietary Se intake. Other parameters that will be included are demographics, medications, wound debridement procedures, invasive devices, mode of nutrition support, kilocalorie and protein intake, weekly weights, neurological status (as routinely assessed by the clinical team) and routine laboratory studies.

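### The repeated measures ANOVA is promised at 5% but names no sphericity correction or covariance model for up to 8 weekly values, so the time and group-by-time tests are not secured at that level

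*Combined protocol and SAP*

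**What the plan says.** The statistical text at the end of section V.D (Selenium Analysis) makes an error-rate promise: "A 2-sided statistical test will be used for all analyses and the overall type-I error rate will be controlled at the 5% level". For each of the three dependent variables, "a 2-way repeated measures ANOVA will be used to examine the difference among groups and over time (primary hypothesis"), with Tukey as the post-hoc test. Section V.C (Data Collection) sets the schedule: "Plasma and urine Se and plasma Gpx will be measured weekly from the time of admission for a maximum of 8 weeks", or until 95% wound closure if that comes sooner. Section IV.B fixes the design: "25 subjects will be in each group (total of 75 subjects").

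Section V.D also keeps every enrolled child in the analysis, says that confounders will enter the models, and names SAS without a procedure. Nowhere do the documents mention sphericity, a Greenhouse-Geisser or Huynh-Feldt correction, a multivariate test, or a covariance structure for the weekly values.

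**The concern.** The univariate F tests for time and for group-by-time have their nominal level only if the means are equal and sphericity also holds, meaning that the differences between any two weeks all have the same variance. Weekly values from one child are plausibly more alike in neighbouring weeks than in distant ones, and that pattern breaks sphericity. The tests can then reject too often although no mean differs. Tukey's procedure adjusts pairwise comparisons and does not address this.

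Group-by-time is the test that would show the arms separating after the infusion starts, so a false signal there could be read as an effect of supplementation. The problem arises with complete data in a single variable. It is therefore separate from missing weeks and from testing three variables.

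**Working it through.** **The plan's own figure.** Section V.D states "The values used were 1.96 for a significance level of 5% and 0.8416 for a power of 80" (per cent). Its standardised difference compares two plasma selenium means: the pilot value of 1.08 µmol/L and the healthy-child value of 1.35 µmol/L. The divisor is the pilot standard deviation of 0.34. So Δ = (1.35 − 1.08)/0.34 = 0.27/0.34 = 0.794, and n = 2(1.96 + 0.8416)²/0.794² = 24.89, rounded up to 25 per group. The stated figure is reproduced. It is a two-mean comparison that does not use the repeated values, so this point does not change it.

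**Inputs for the error rate.** From the documents: g = 3 groups of 25, so N = 75 with N − g = 72 between-child error degrees of freedom; T = 8 weekly values at most; nominal level 5%. Assumed, because the documents do not give them: normal errors, the week-to-week correlation, and the share of variance that is independent weekly noise.

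**Formulas.** Let λ₁…λ₇ be the non-zero eigenvalues of the week-centred covariance matrix. With no true differences,

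F = [Σλⱼχ²(q)/q] / [Σλⱼχ²(72)/72], with q = 1 for time and q = 2 for group-by-time.

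The uncorrected tests refer F to (7, 504) degrees of freedom for time and (14, 504) for group-by-time, since 2 × 7 = 14 and 72 × 7 = 504. That is exact only when all λⱼ are equal. The departure is measured by ε = (Σλⱼ)²/(7Σλⱼ²), which is 1 under sphericity. At AR(1) correlation 0.7, ε = 0.549, so the group-by-time test behaves roughly as if it had 14 × 0.549 = 7.7 and 504 × 0.549 = 277 degrees of freedom.

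**Null rejection rates, 8 complete values, no independent noise** (400,000 draws per cell):

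| AR(1) correlation | ε | Time | Group-by-time |
|---|---|---|---|
| sphericity met | 1.00 | 5.0% | 5.0% |
| 0.3 | 0.88 | 5.9% | 5.9% |
| 0.5 | 0.72 | 7.1% | 7.5% |
| 0.7 | 0.55 | 8.8% | 9.6% |
| 0.8 | 0.47 | 9.5% | 10.7% |
| 0.9 | 0.40 | 10.5% | 11.9% |

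Adding a stable child effect leaves ε unchanged. In a direct simulation at correlation 0.7, with 40% of the variance between children, the rates were 8.7% for time and 9.6% for group-by-time.

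**With independent weekly noise.** With 30% of the variance as noise, group-by-time rejects about 5.4-6.9% across AR(1) 0.3-0.9. With 50% noise it rejects about 5.3-5.8%.

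**Shorter series.** With 4 complete values and no noise, group-by-time is at most about 7.5% (time 6.9%), reached at correlation 0.9.

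**Group main effect.** In the direct simulations (6,000 trials per cell) its rejection rate stayed between 4.4% and 5.3%.

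**Effect of a correction.** With 8 complete values and AR(1) 0.5-0.9, Greenhouse-Geisser correction gives 4.6-5.1% for group-by-time and 4.2-5.4% for time.

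**The case against.** A reader might infer that the primary analysis runs at about twice its promised error rate. The documents do not support that. In the table above, group-by-time reaches 10% only between correlations 0.7 and 0.8, and time only between 0.8 and 0.9. Both results need about 8 complete values and no independent noise. Section V.C includes 24-hour urine collections, some from diapers, and every assay adds some measurement error. Independent noise pulls the pattern back towards sphericity, and at a 30% share most of the inflation is gone. The noise share is as unknown as the correlation.

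The plan also does not say that its ANOVA will be uncorrected. It names SAS but no procedure, keeps children with uneven series and adds covariates, so a model-based analysis is a possible reading. It never names an interaction test; group-by-time is inferred from testing groups and time together. The test of average group difference holds its level. These points stand. They limit the size of the problem and make the defect one of an unsecured promise.

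The argument that early end of follow-up removes the problem does not stand. One check drew series lengths from an assumed lognormal stay matching the pilot's 50 ± 40 days (Table 4), capped at 8 weeks, with noise-free AR(1) and lengths unrelated to outcome. Group-by-time rejected 7.8%, 9.2%, 11.4% and 16.9% at correlations 0.3, 0.5, 0.7 and 0.9. The stay distribution is assumed, but the result shows that the complete-data rates are not a ceiling.

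**Conclusion.** The concern holds in a limited form. As written, the plan does not secure 5% for the time and group-by-time tests, because it states neither a correction nor a covariance model. If the uncorrected tests are used with 8 complete values, a fair range for group-by-time is about 5% to 12%: near the bottom when 30-50% of the variance is independent noise, and near the top only under strong noise-free serial correlation. For time the upper end is about 10.5%.

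The range rests on the assumed correlation and noise share, normal errors and the uncorrected reading of the plan. It does not show that a conclusion about the average difference among groups is unsafe, and it does not alter the 25 per group.

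**What to change.** In the statistical text of section V.D, replace the 2-way repeated measures ANOVA with a likelihood-based mixed model for repeated measures (SAS PROC MIXED) containing group, week and group-by-week. This keeps all enrolled children with uneven series. Specify an unstructured within-child covariance with Kenward-Roger degrees of freedom.

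Name in advance the fallback if it does not converge: a random child intercept plus AR(1) plus residual error, or a simpler structure with empirical standard errors. AR(1) alone, even with unequal variances, has no stable child effect and is a weak fallback. Take the Tukey comparisons from the fitted model.

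Use Greenhouse-Geisser p-values only as a sensitivity analysis in children with complete series. In its standard form that analysis drops children whose follow-up ends early, which conflicts with the plan's inclusion of everyone enrolled.

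The cost is a few sentences, in software already named. Expect slightly larger p-values for time and group-by-time. Convergence may fail, since 8 weeks give 8 × 9/2 = 36 covariance parameters for 75 children with uneven follow-up. The error rate of the mixed model was not simulated here; only the degrees-of-freedom corrections were.

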Table 3. ASPEN guidelines for Se content of parenteral nutrition.

Age Group	Se
Neonates 3-10 kg	2 ug/kg/day
Children 10 – 40 kg	1 – 2 ug/kg/day
Children > 40 kg	40 – 60 ug/day

Selenium Requirements

The Third National Health and Nutrition Examination Survey (NHANES III) reports that Americans consume 106 micrograms of Se per day (42). The

current Recommended Dietary Allowance (RDA) for Se is 20 µg/day for 1-3 year old children, 30 µg/day for 4-8 year old children, 40 µg/day for 9-13 year old children, and 55 µg for children > 13 and adults (31). Recommendations among adults are based on the amount of Se needed to achieve optimal GPx activity. Pediatric recommendations were determined by extrapolating from adult data. An exact recommendation for Se during an acute illness is not known.

Assessment of selenium status

Accurate determination of Se status during critical illness should include plasma Se, plasma Gpx, and urine Se (43). It is especially important to measure Gpx activity because it represents the functional marker of Se status. Gpx activity appears to plateau after a certain Se intake has been reached (44) and is not affected by the form of Se ingested(44).

B. Previous research to support proposed research

Preliminary study: Selenium status of pediatric patients with burns

A prospective study, designed to assess the longitudinal Se status of pediatric burn patients, was conducted by this research team. Twenty patients admitted to Shriners Hospital in Boston, MA with burns exceeding 15% of their total body surface area (TBSA) were studied longitudinally for 8 weeks following admission or until 95% wound closure was achieved (determined by the attending physician using a burn diagram). Dietary Se intake from all forms of nutrition (oral, enteral, parenteral) was calculated daily and plasma and urine samples were collected weekly. Plasma Se, plasma glutathione peroxidase (GPx) activity and urinary Se were determined. Demographic data is featured in Table 4.

Table 4. Demographics (N = 20)

	Mean \pm Standard Deviation	Range
Gender	15 males 5 females	
Age (years)	6.5 \pm 5.3	0.33 – 16
Length of Stay (days)	50 \pm 40	11 – 161
Initial %TBSA	42 \pm 21	15 - 93
% Full Thickness	27 \pm 27	0-90
Type of Burn	15 flame 5 scald	

The mean dietary Se intake throughout the 8 week study was 60 \pm 39 µg/day. Weekly selenium intake did not change significantly over the eight-week study

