(Figure 1). All subjects consumed greater than the RDA for Se (Table 5). They also consumed more Se than recommended by the ASPEN (27).

Table 5. Dietary Se Intake and % AI According to Age

Age (years)	Number of Subjects	Mean Se Intake (ug/day)	Mean Se Intake (ug/kg/day)	% RDA
1-3	8	40	2.9	200
5-8	2	62	2.5	201
9-13	7	75	1.6	183
14-18	2	83	1.4	151

Plasma Se (mean = $1.08 \pm 0.34 \text{ } \mu\text{mol/L}$) did not change throughout the entire study. However, 82% of the total weekly samples were below the $1.35 \text{ } \mu\text{mol/L}$ plasma selenium level reported in healthy American children ages 1-18yrs (Figure 2). Higher plasma selenium was also correlated with a lower incidence of infection ($p = 0.043$).

The mean plasma glutathione peroxidase (GPx) level over the eight weeks was $3.29 \text{ Units/mg protein} \pm 1.42$. Furthermore, 40% of all weekly plasma GPx samples were below the $2.8-3.4 \text{ U/g protein}$ range established in healthy American girls ages 11-14 (34) . No statistical differences were found throughout the eight weeks.

There was no significant change in urinary selenium levels between weeks. The mean urinary selenium level throughout the eight-week study was $65.9 \text{ } \mu\text{g/L} \pm 50$, which is higher than the mean selenium intake from diet $60 \text{ } \mu\text{g/L} \pm 39$. A majority of the observed urinary selenium levels were higher than those reported ($28.7 \text{ } \mu\text{g/L} \pm 8.3$) in healthy American children ages 5-18 years (35).

In summary, these results indicate that selenium status in pediatric burn patients, as measured by plasma and urine selenium concentrations and plasma GPx activity, was inadequate throughout the eight weeks following thermal injury. Additionally, these results suggest that maintaining normal blood concentrations of selenium and GPx activity following burn injury reduce the incidence of infection. This data was presented at the American Burn Association Annual meeting in March 2007 and published in the Journal of Trauma in 2010.

Figure 1. Dietary Selenium. Selenium intake did not change significantly over the eight week study. Intake ranged from 100-400% the AI/RDA (based on age).

[figure not shown]
[figure not shown]

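### The plan promises an overall 5% type-I error but gives no rule across its three primary ANOVAs, so the 5% is not secured across the primary variables

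*Combined protocol and SAP*

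**What the plan says.** All the relevant statistical text is in section V.D (Selenium Analysis), after the sample size formula.

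- The promise is that "the overall type-I error rate will be controlled at the 5% level", with two-sided tests throughout.
- For the primary hypothesis: "For each dependent variable (plasma selenium, urinary selenium, plasma GPx activity) a 2-way repeated measures ANOVA will be used" to look at differences between groups and over time.
- The only multiplicity procedure named is Tukey's, which "will be utilized as the post-hoc test".
- The sample size rests on plasma selenium alone. Of the standardized difference the plan says: "This was calculated by subtracting the mean plasma Se determined in our pilot study", with the mean in healthy children as the other term.
- For the secondary hypothesis: "An ordinal logistic regression will be performed to determine the relationship between the incidence of infection" and the markers, age, burn size and treatment group. The plan does not say whether this regression falls under the overall 5%.

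Elsewhere, section I.A (Assessment of selenium status) says: "Accurate determination of Se status during critical illness should include plasma Se, plasma Gpx, and urine Se". It adds: "It is especially important to measure Gpx activity because it represents the functional marker of Se status". The pilot summary in I.B describes selenium status "as measured by plasma and urine selenium concentrations and plasma GPx activity". The hypothesis in section II concerns selenium status in general, and Aim 1 lists all three markers. The study endpoint in V.D is a rule for when a child's participation ends; it does not designate an outcome.

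**The concern.** An overall error rate needs a defined family of tests and a rule for what counts as success. Here three variables share the primary label, and each two-way ANOVA yields group, time and group-by-time effects. Tukey controls comparisons among means within one ANOVA and does nothing across the three.

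Without a rule fixed in advance, a significant result on any one variable, or on either between-arm effect, could later be reported as confirming the primary hypothesis at 5%. A reader could not tell from the plan whether the three results were meant jointly or as alternatives, and so could not check the claim. The time effect alone is not a comparison between arms and cannot answer the question of supplementation, yet the plan does not exclude it as the deciding test.

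**Working it through.** **Inputs from the plan.** Overall two-sided error 5%; three primary variables; three arms of 25; pilot mean 1.08, reference mean 1.35 and SD 0.34 µmol/L; no interim analyses.

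**Step 1: the plan's own figure.** Δ = (1.35 − 1.08)/0.34 = 0.794. n = 2 × (1.96 + 0.8416)²/0.794² = 24.9, rounded up to 25 per group. This reproduces. It spends the full 5% on plasma selenium and makes no allowance for two further primary variables.

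**Step 2: error under each success rule.** The documents give neither the rule nor the correlations between markers, so both are assumed. The correlated cases are simulated: three arms of 25, one value per child, equal correlation between variables, overall F test with 2 and 72 df at 5% each.

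| Rule and true state | Independent | Correlation 0.5 | Correlation 0.9 |
|---|---|---|---|
| Any one of three counts, none responds | 1 − 0.95³ = 14.3% | about 12.7% | about 8.5% |
| Any one counts, one variable responds (two nulls) | 1 − 0.95² = 9.75% | about 9.2% | about 7.1% |
| Any one counts, two respond (one null) | 5% | 5% | 5% |
| All three must be significant | at most 5% | at most 5% | at most 5% |

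Whatever the dependence, the first row cannot exceed 3 × 5% = 15%, nor the second 2 × 5% = 10%.

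**Step 3: more than one effect on one variable.** If either the group or the group-by-time test on plasma selenium counts, the error is 1 − 0.95² = 9.75% for independent tests, and at most 10%.

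**Step 4: does an ordered test hold 5%?** Take plasma selenium first, then GPx only if plasma selenium is significant. If plasma selenium is null, the first test stops the sequence 95% of the time. If it responds, a false GPx result has probability at most 5%. So 5% holds for the overall tests, and a third step for urinary selenium does not change that.

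It does not hold once Tukey dose comparisons are also counted. Suppose one dose moves plasma selenium strongly, the other does not, and GPx is null. The null dose pair on plasma selenium gives a false Tukey result about 2% of the time, and GPx is still tested at 5%: 1 − 0.98 × 0.95 = 6.9% if independent. Simulated with a 1.5 SD one-dose effect, the range over correlations 0.9 to 0 is about 5.8% to 6.9% with two steps. With three steps (one dose moves plasma selenium and GPx, urinary selenium null) it is about 6.1% to 8.6%.

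**The case against.** The strongest reply is that the promise may already be met. Sections I.A, I.B and II treat the three markers together as selenium status. If the hypothesis is joint and all three must be significant, the error is at most 5%. Overall may also mean only across the three arms, which Tukey covers within a variable. Or plasma selenium may be primary in effect, since the sample size uses nothing else. Finally, a complete null may be unrealistic: the paediatric trial cited in I.B reported lower plasma selenium and GPx in its control group, at other doses. If both respond here, one null is left and there is no excess across variables.

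Much of this stands. A reader might infer that the trial's error rate is 14.3%, or that the plan breaks its promise. The documents support neither. They never say that each ANOVA is tested at 5% or that any one result suffices, and markers of one nutrient need not be independent.

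What does not stand is that the replies settle the matter. They imply different success criteria from the same text: all three, each separately, or plasma selenium alone. The plan gives all three variables the same primary label, analyses each on its own, and singles out GPx as the functional marker. It chooses none of these readings.

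**Conclusion.** The concern holds as a missing rule. The plan states an overall 5% and names no procedure that secures it across its three primary variables or across the effects within each ANOVA. It also leaves open whether the infection regression is covered.

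The possible size runs from no excess (one true null, or all three required) to 14.3% (any one counts, each at 5%, independent tests, no variable responds), with about 12.7% and 8.5% at correlations 0.5 and 0.9. These figures rest on assumptions outside the documents; they show the gap and do not predict the trial's error rate. The trial is not invalidated, but the rule should be settled before unblinding.

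A reader might also infer that ordering the tests brings every dose claim under 5%. Step 4 shows that it does not.

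**What to change.** Add a few sentences to V.D:

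1. Name plasma selenium, the only variable in the sample size, as the primary variable.
2. Name one between-arm effect, group or group-by-time but not time alone, as the deciding test at two-sided 5%.
3. Test the same effect for GPx at 5% only if plasma selenium is significant. Urinary selenium may be a third step on the same terms, or supportive.
4. Place the infection regression outside the 5% claim.
5. State that the 5% applies to these ordered overall tests and that Tukey dose comparisons are controlled within each variable only. With a strong one-dose effect, counting them as well gives about 6% to 7% with two steps or 6% to 9% with three.

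Putting GPx first would hold the same 5%, but the sample size was not built on it. An explicit all-three rule would also honour the promise. The simplest alternative is to replace overall with per variable and state that there is no adjustment across outcomes.

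The ordered version needs no extra children or samples and leaves plasma selenium at its full 5%, so that test loses no power. The price is that there is no confirmatory GPx claim if plasma selenium is not significant, and urinary selenium becomes supportive or third although Aim 1 lists it. An equal split would cost more: at 0.05/3 the plan's two-group formula gives 2 × (2.394 + 0.8416)²/0.794² = 33.2, or 34 per group instead of 25. That is a single-measurement figure and does not describe the planned repeated measures analysis.
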